Title: Revitalizing Cognition in Older Adults at Risk for Alzheimer's Disease
using Near Infrared Photobiomodulation

[figure not shown]
8-1-2025

NCT04018092

STATISTICAL DESIGN AND POWER

Sample Size Determination/Power Analysis

The sample size calculation was based on our pilot results of all primary and secondary measures in Aim 1 and Aim 2. Here we use ARENA, our primary outcome that is being tested in Aim 1 (see H1.1) to illustrate the power calculation procedure. From our pilot data, the mean difference of ARENA score changes between active stimulation group ($n = 8$) and sham ($n = 5$) group was 0.58. Based on a pooled standard deviation of 0.55, the standardized effect size (Cohen's d) is $d=1.06$. Similarly, we calculated the standardized effect sizes of our secondary outcome variables, including working memory (H1.2, $d=0.67$); prefrontal cortex ATP (H2.1, $d=0.48$); temporal lobe ATP (H2.1, $d=0.5$); prefrontal cortex connectivity (H2.2, $d=1.3$); and temporal lobe connectivity (H2.2, $d=1.1$). Based on our experience of 10% attrition in a clinical trial with three months of intervention for the ACT study (MPI: [name]; PI UA Field Site: [name]) that is currently underway at the UF and UA field sites, we conservatively assumed 15% attrition in the power calculations for the current proposal. At 5% alpha level and assuming the 15% attrition rate, the power trajectories for different measures with respect to number of samples per treatment group are shown in the above figure. In order to guarantee that all these primary and secondary measures have more than 80% power, we plan to enroll a total of 168 participants (84 per group, shown as the dashed line in the above figure). This large sample size will also ensure sufficient statistical power for the exploratory analysis of Aim 3, where we will examine potential mediators and moderators in relation to the intervention response. Note that we are powering the study based on a 2-week session and the actual effect sizes (from a 12-week NIR stimulation session) will likely exceed these minimal estimates.

Statistical Analysis

All data will be checked for out-of-range values, and distributional forms (normality, homogeneity of variance). Decisions regarding parametric vs nonparametric statistics will be based on the results of those analyses. Standard summary statistics will be provided for pre, post- and follow-up time points. The intention-to-treat (ITT) principle will be applied whereby all randomized patients who complete the baseline assessment will be analyzed according to their assigned interventions. For studying the relationship between longitudinal outcomes and NIR stimulation effects, we will fit linear mixed effects models with subject specific random effects to account for the within subject correlation, using R software *lmer* package¹⁵⁸. Linear mixed model is robust against missing data if they are missing at random (MAR)¹⁵⁹. Baseline outcomes and covariates including age, sex, education, and other potential confounders (listed in Exploratory Aim 3) will be adjusted to take account for confounding effects. If multiple hypotheses are investigated simultaneously, multiple comparisons will be properly adjusted by using Benjamini-Hochberg correction¹⁶⁰. Below we describe how these statistical models fit the specific aims in this proposal.

Analyses for Aim 1: To test the hypothesis that the active NIR stimulation will result in greater pre-post intervention improvement in cognition (episodic memory, executive function) relative to the sham group, we will fit the following linear mixed model:

$$y_{ik} = \mu + \alpha_i + \beta \mathbb{I}(z_i = 1) + \sum_{l=0}^L \gamma_l x_{il} + \eta \mathbb{I}(k = 2) + \theta \mathbb{I}(z_i = 1, k = 2) + \varepsilon_{ik}, \alpha_i \sim N(0, \sigma_0^2), \varepsilon_{ik} \sim N(0, \sigma^2) \quad (1)$$

where y_{ik} is the outcome variable (e.g., ARENA score for Aim 1) for subject i and visit k ($k = 1$ for post-intervention and $k = 2$ for 3-month follow-up); μ is the intercept term; $\alpha_i \sim N(0, \sigma_0^2)$ is the random effect with variance term σ_0^2 for subject i ; z_i is the treatment indicator with $z_i = 0$ for sham group and $z_i = 1$ for active

stimulation group, β is the post intervention treatment effect (active stimulation effect compare to sham group) and $\mathbb{I}(\cdot)$ is the indicator function which equals to 1 if the argument inside (\cdot) is true and equals 0 otherwise; x_{il} is the l^{th} covariates for subject i with $l = 0$ for baseline level (e.g. baseline ARENA for Aim 1) and $l = 1, 2, \dots, L$ for L covariates (i.e., age, sex, education...); η is the time effect of 3-month follow-up compared to post-intervention visit; θ is the interaction effect between follow-up and active stimulation; $\varepsilon_{ik} \sim N(0, \sigma^2)$ is the error term with variance σ^2 . In equation (1), β is the active stimulation effect for post-intervention, and we will perform the statistical hypothesis testing ($H_0: \beta = 0$) to provide its p-value, point estimate and confidence interval. Similarly, $\beta + \theta$ is the active stimulation effect after 3-month follow-up, where p-value, point estimate and confidence interval will be similarly obtained by testing the null hypothesis $H_0: \beta + \theta = 0$. Note that equation (1) will be applied to all measures in Aim 1 including the primary outcome (ARENA), secondary outcomes (working memory), and other exploratory outcomes (verbal fluency, mnemonic similarity, auditory verbal learning test, and Stroop color word test).

Analyses for Aim 2: To test the hypothesis that NIR stimulation will result in greater pre-post intervention improvement in neuroimaging (31P MRS for ATP and rs-fMRI for connectivity) relative to the sham group, we will fit the following linear mixed model:

$$y_{ik} = \mu + \alpha_i + \beta \mathbb{I}(z_i = 1) + \sum_{l=0}^L \gamma_l x_{il} + \varepsilon_{ik}, \alpha_i \sim N(0, \sigma_0^2), \varepsilon_{ik} \sim N(0, \sigma^2) \quad (2)$$

Equation (2) is similar to equation (1), with the adjustment of the same set of covariates, except that the equation (2) doesn't have the 3-month follow-up. β is the active stimulation effect for post-intervention, for which we will perform the statistical hypothesis testing ($H_0: \beta = 0$) to provide its p-value, point estimate and confidence interval. Note that equation (2) will be applied to all measures in Aim 2 including secondary outcomes involving ATP from 31P MRS (H2.1) and connectivity from, rs-fMRI (H2.2).

Analysis for Exploratory Aim 3: We want to further explore whether APOE $\varepsilon 4$ carrier status, vascular comorbidities, Fitzpatrick skin type questionnaires, processing speed, and mood are potentially confounders, moderators, or mediators. To examine confounders, we will directly adjust these variables as covariates in the linear mixed model in equation (1) and equation (2). A statistically significant covariate effect will imply the potential confounding roles of these variables. To examine moderators, we will include these variables and their interactions with the intervention effect (one variable at one time) in equation (1) and equation (2). A statistically significant interaction effect will imply the variable can be a moderator. To examine mediators, we will perform mediation analysis¹⁶¹⁻¹⁶². The mediation effects of these variables and their 95% confidence interval will be determined using the R *mediation* package¹⁶³.

For each of the specific aims listed above, we will further conduct exploratory analysis stratifying by sex, to examine its relevant biological effect. In other words, we will disaggregate the data by sex and evaluate the active stimulation effects for male and female, respectively.

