*Note that we are highly experienced in working with older adults who are identified as experiencing current major depression or other psychological disturbances or who perform below cutoff on standard cognitive screening measures. [name], at the UF site, is a boarded clinical neuropsychologist who has been working with this clinical population for over 30 years. Two Co-I's ([name], [name]) are experienced neurology clinicians. All are experienced with diagnosis and treatment of mood and cognitive disorders. Similar clinical expertise exists at the University of Arizona. Discussions will be held with individuals of concern and recommendations will be made to appropriate health care providers with permission of the participant and in line with standards of care. Specifics regarding how we address suicidality is described on page 19 of this protocol.

Sample Size, Attrition, Power, and Intent to

Treat. Our planned sample size includes 168 cognitively normal individuals (N=84 Active/N=84 Sham intervention). This sample size was determined directly from the effect sizes of our pilot data. Importantly, the study was powered to assess hypotheses proposed in Specific Aims 1 and 2, with 80% power. The vertical dash line in the figure to right shows the projected point at which 80% power will be achieved at $p=0.05$, two

tailed, relative to a sample size of the two treatment groups derived from the effect sizes of our pilot data. Based on our previous intervention studies with older adults, we anticipate a 30% attrition rate and up to 82 screen failures.

To account for screen failures and study attrition, we anticipate consenting up to 300 individuals.* Intent to treat analysis will be used to reduce selective attrition bias; participants who are unwilling/unable to complete the intervention will be encouraged to attend the post intervention testing. *(With informants, the number of involved individuals is doubled.)

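### The SAP's power guarantee assumes 15% attrition, but the protocol anticipates 30% for the same 84 per arm, which decides whether the two ATP outcomes reach 80% power

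*SAP*

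**What the plan says.** **SAP, Sample Size Determination/Power Analysis.** The calculation cites "experience of 10% attrition in a clinical trial with three months of intervention" in another study by the team, and from that "we conservatively assumed 15% attrition in the power calculations for the current proposal". The aim of the sample size is given as "In order to guarantee that all these primary and secondary measures have more than 80% power". The number that follows from it is an enrolment figure: "we plan to enroll a total of 168 participants", split equally between the arms (84 each). The secondary measures listed there include prefrontal ATP (d = 0.48) and temporal ATP (d = 0.50), the two smallest assumed effects.

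**Protocol section 7.2, paragraph on sample size, attrition and power.** The same 84 per arm appears, with the statement that "the study was powered to assess hypotheses proposed in Specific Aims 1 and 2, with 80% power". The attrition figure differs: "Based on our previous intervention studies with older adults, we anticipate a 30% attrition rate and up to 82 screen failures". It then says: "To account for screen failures and study attrition, we anticipate consenting up to 300 individuals".

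**Elsewhere in the protocol.** The opening summary and section 5 both give 168 as the number randomised. The first paragraph of section 7.2 counts participants and informants together. It starts from 336 people and allows for 100 drop-outs and up to 350 screen failures.

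**The concern.** Two documents make the same power claim for the same sample size with attrition rates that differ by a factor of two. Each rate is attributed to the team's own experience with earlier studies. Nothing explains the difference.

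The margin is thin where it counts. The two ATP outcomes have the smallest assumed effects, so they set the sample size, and the SAP's 15% leaves prefrontal ATP only just above 80%. ATP is also the mechanism by which the intervention is proposed to work. A null ATP result would be read against a stated guarantee of more than 80% power, and the documents do not show that this guarantee holds under the protocol's own attrition figure.

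**Working it through.** **Inputs.** From the SAP: 84 per arm, 5% alpha, 15% attrition, and d = 0.48 (prefrontal ATP), 0.50 (temporal ATP), 0.67 (working memory), 1.06 (ARENA), 1.3 and 1.1 (connectivity). From protocol section 7.2: a two-tailed test, 30% attrition, 82 screen failures, 300 consented. The pilot effect sizes are taken as given.

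**Method.** Two-sample t test on change scores with n evaluable per arm: noncentrality d × √(n/2), 2n − 2 degrees of freedom, two-sided 5%. Expected n may be fractional.

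**Step 1: the SAP's own figure.** 84 × 0.85 = 71.4 per arm. For prefrontal ATP the noncentrality is 0.48 × √35.7 = 2.87 and power is 81.3%. For temporal ATP it is 0.50 × √35.7 = 2.99 and power is 84.3%. The SAP's claim reproduces.

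**Step 2: the protocol's rate under each reading of 168.**

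| Reading | Evaluable per arm | Prefrontal ATP | Temporal ATP |
|---|---|---|---|
| 168 randomised, 15% lost | 84 × 0.85 = 71.4 | 81.3% | 84.3% |
| 168 randomised, 30% lost | 84 × 0.70 = 58.8 | 73.3% | 76.7% |
| 300 − 82 = 218 randomised, 30% lost | 218 × 0.70 / 2 = 76.3 | 83.8% | 86.6% |
| 168 completing | 84 | 87.1% | 89.7% |

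At 58.8 per arm, working memory has 95.0% power, and ARENA and both connectivity measures exceed 99%.

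**Step 3: how much loss 84 per arm can absorb, in whole participants.** Prefrontal ATP needs 70 completers per arm (80.5%; 69 gives 79.9%), so at most 14 of 84 may be lost, or 16.7%. Temporal ATP needs 64 (80.1%; 63 gives 79.5%), so at most 20 of 84, or 23.8%. The protocol's 30% exceeds both. At 30% loss, 70 per arm requires 140 / 0.70 = 200 randomised.

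**Step 4: which reading the protocol supports.** 30% of 168 is 50, and 168 + 50 + 82 = 300, which is the consent ceiling. That points to drop-outs being added on top of 168. The statements that 168 will be randomised point the other way, and so does the SAP, whose 168 already contains the 15% loss.

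**Step 5: baseline adjustment.** SAP equation (2) adjusts for the baseline value. With equal pre and post SDs and pre-post correlation r, the effect on the adjusted scale is d × √(2/(1 + r)), with 2n − 3 degrees of freedom. The documents give no r, so a range is shown for 58.8 per arm:

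| Assumed r | Prefrontal ATP | Temporal ATP |
|---|---|---|
| 0.5 | 85% | 87% |
| 0.7 | 80% | 83% |
| 0.9 | 75% | 79% |

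Power stays at 80% or more for r up to about 0.70 (prefrontal) or 0.84 (temporal).

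**The case against.** The strongest reply is that 73% and 77% combine 30% attrition from one protocol sentence with 168 randomised from elsewhere, and ignore the next sentence, which raises the number consented to cover that attrition. The opening paragraph of section 7.2 supports this. Its 100 drop-outs include informants, so they amount to about 50 participants, again 30% of 168. On that reading power is at least 84%. This stands as a plausible reading, but it does not remove the conflict: 168 would then mean completers in the protocol and enrolled participants in the SAP. The consent counts are also weak evidence, since 336 + 350 + 100 = 786 while the stated ceiling is 768.

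The two rates may also measure different losses. The SAP's rate comes from a trial with a three-month intervention, which matches the imaging window. The protocol's 30% has no time window, and this trial has a further 3-month follow-up. The protocol adds that "participants who are unwilling/unable to complete the intervention will be encouraged to attend the post intervention testing", so some who stop treatment may still be scanned. This is possible, and it is what the documents need to state.

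The effect sizes come from a pilot of 8 versus 5, only some of whom were imaged. Even with all 13, an approximate 95% interval around d = 0.48 runs from −0.65 to 1.61. Attrition is therefore a small part of the real uncertainty. That is a separate weakness. It does not make the two rates agree.

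The SAP's conditional Benjamini-Hochberg correction enters neither the SAP's calculation nor this one. It could lower power: at an illustrative per-test alpha of 0.025 (an assumption), 58.8 per arm gives 63% and 67%, and 76.3 per arm gives 76% and 79%.

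Finally, only the two ATP outcomes are at risk, and the SAP reports estimates with confidence intervals. This limits the consequence.

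**Conclusion.** The concern holds. The guarantee rests on an attrition rate that the protocol contradicts for the same sample size and the same power claim, and neither document resolves it. This does not show that the trial is underpowered. Power for prefrontal and temporal ATP is 73% and 77% if 168 are randomised and 30% lack post-intervention data. It is 84% and 87% if 218 are randomised with the same loss, and 87% and 90% if 84 per arm complete.

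These figures assume the SAP's pilot effect sizes, two-sided 5% without multiplicity correction, no baseline adjustment, and that attrition means no post-intervention measurement. The primary outcome, working memory and connectivity are not affected. The point should be fixed. Confidence is medium, because the intended reading of 168 cannot be settled from the documents.

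**What to change.** In protocol section 7.2 and the SAP, state the same four things:

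- one expected rate of loss of post-intervention data, with its time window and basis;
- whether 168 is the number randomised or the number completing;
- whether drop-outs are replaced;
- the expected completers per arm.

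Then replace the guarantee sentence with the power that follows.

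- **If 168 are randomised with 30% loss:** *With 168 randomised and 30% loss of post-intervention data (about 59 per arm), power at two-sided 5%, without baseline or multiplicity adjustment, is about 73% for prefrontal ATP, 77% for temporal ATP, 95% for working memory, and above 99% for ARENA and connectivity.*
- **If drop-outs are added on top:** give the number randomised and the matching power (84% and 87% for 218 randomised with 30% loss; 87% and 90% for 84 completing per arm), and correct the statements that 168 will be randomised.
- **If 15% is kept:** correct the 30% in section 7.2 and give its basis.

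A baseline-adjusted figure may be added if its assumed pre-post correlation is stated. The consent totals in section 7.2 should be brought into line in the same edit.

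The cost is wording in two documents and possibly a less favourable stated power for two secondary outcomes. Restating the figures adds no participants and changes no analysis.

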Aim 1: To evaluate whether NIR-PBM stimulation can improve cognitive function in older adults with increased risk for Alzheimer's disease. Specifically, we plan to test whether 12 weeks of NIR stimulation, relative to sham, improves performance on memory (primary outcome) and executive function tasks sensitive to hippocampal and frontal brain function in older adults with increased risk for Alzheimer's disease. We hypothesize that NIR stimulation will result in greater improvement on tasks of H1.1) episodic memory and H1.2) executive function relative to sham. The primary outcome measure will be a spatial navigation task (ARENA), a human analogue to the Morris Water Maze¹⁷, that is sensitive to hippocampal function. A secondary cognitive outcome measure will be the executive function working memory composite score from the NIH Examiner battery known to be sensitive to frontal brain function.

Aim 2: To evaluate whether NIR-PBM intervention enhances brain function and connectivity in those at increased risk for Alzheimer's disease. We plan to test whether 12 weeks of NIR stimulation leads to enhanced markers of 31-P MRS ATP and rs-fMRI functional connectivity in older adults with increased risk for Alzheimer's disease. We hypothesize that: H2.1) NIR stimulation will produce pre-post increases in frontal and medial temporal brain markers of MRS ATP function and

H2.2) pre-post increases in functional connectivity in frontal and medial temporal lobe mediated resting state brain networks.

Exploratory Aim: To examine how baseline demographic, mood, vascular risk, genetic, and neuroimaging factors influence individual differences in cognitive outcome for NIR-PBM intervention. We plan to evaluate how baseline MRI white matter abnormalities, apolipoprotein E (APOE) ε4 status, and metabolic/vascular risk factors of hypertension and diabetes influence cognitive outcomes after 12 weeks of NIR stimulation. Additional factors include demographic (age, education, gender), mood status, and general processing efficiency. For this exploratory aim, we hypothesize that: HE.1) greater white matter lesion load on FLAIR MRI, HE.2) metabolic-vascular risk factors of hypertension and diabetes, and HE.3) APOE ε4 status will each predict poorer NIR-PBM outcomes in memory and executive function.

[figure not shown]
7. Research Plan

7.1 Design Overview.

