- Sensory loss (vision, hearing) or motor deficits that would preclude participation in the experimental tasks or neuropsychological assessment
- English as a second language or Non-English speaking
- Inability to undergo brain imaging due to claustrophobia or implants such as pacemakers, heart valves, brain aneurysm clips, orthodontics, non-removable body jewelry, or shrapnel containing ferromagnetic metal
- Previous major strokes or other known significant brain abnormalities or diseases affecting the brain and/or cognition (e.g., Parkinson disease, multiple sclerosis, seizure disorder, brain surgery, moderate TBI, REM Behavior Sleep Disorder, untreated sleep apnea, etc.)
- Unstable and uncontrolled medical conditions (metastatic cancer, HIV, moderate-severe kidney disease, uncontrolled diabetes, uncontrolled hypertension, severe cardiac disease, etc.). No current cancer diagnosis
- Current or past history of major psychiatric disturbance including schizophrenia, or active psychosis, bipolar disorder, current major depressive episode, current alcohol or substance abuse or history thereof within the past six months. Scores > 20 on the Beck Depression Inventory-II. We are not excluding individuals who are taking antidepressant or anti-anxiety medications. However, use of these medications will be recorded and data analyzed in post-hoc analyses
- Use of antipsychotics, sedatives, or other medications with significant anticholinergic properties (due to potential influence on memory)
- Use of prescribed 'memory enhancing' medications such as Aricept or Namenda
- Use of photo-sensitive medications such as steroids or retin-A within 15 days of the study intervention.
- Previous participation in a cognitive training study within the last 6 months or current involvement in another study involving cognitive, physical or other intervention at the time of participation.

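### The SAP says 168 participants give enough power for Aim 3, but no calculation supports this, and for binary moderators it holds only if nearly all of an effect as large as the pilot ARENA effect is removed

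*SAP*

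**What the plan says.** The SAP (Sample Size Determination/Power Analysis) derives 84 per group from pilot effect sizes for the primary and secondary measures of Aims 1 and 2. These run from d = 0.48 (prefrontal ATP) to d = 1.3 (prefrontal connectivity). The power curves are drawn "At 5% alpha level and assuming the 15% attrition rate". It then extends the conclusion to the third aim: "This large sample size will also ensure sufficient statistical power for the exploratory analysis of Aim 3".

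Protocol section 7.2 (Sample Size, Attrition, Power, and Intent to Treat) says only that the study was powered for Specific Aims 1 and 2, and it expects 30% attrition.

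Protocol section 6 labels the aim exploratory but gives it directional hypotheses. White matter lesion load (HE.1), hypertension and diabetes (HE.2) and APOE ε4 status (HE.3) are each expected to predict a poorer memory and executive response.

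The SAP (Analysis for Exploratory Aim 3) tests moderators by adding a treatment interaction, one variable at a time: "A statistically significant interaction effect will imply the variable can be a moderator". It plans a separate mediation analysis.

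On the vascular factors, section 6 refers to "metabolic/vascular risk factors of hypertension and diabetes" without qualification. The exclusion criteria in section 7.2 remove "uncontrolled diabetes, uncontrolled hypertension, severe cardiac disease", among other unstable conditions.

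**The concern.** A sample size that just reaches 80% power for a main effect is usually far too small for an interaction of similar size. Here the sample has almost no reserve for the smallest main effect, yet the SAP promises adequate power for a set of interaction tests it never sized.

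The assurance matters because of how a null result would be received. If the APOE or vascular interaction is non-significant, a reader who trusts the SAP may conclude that these factors do not alter response. The data are meant to inform a Phase III trial, so that misreading could reach its eligibility or stratification decisions.

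**Working it through.** **Inputs.** From the SAP: 84 per group, 5% alpha, 15% attrition, pilot d = 0.48 (prefrontal ATP), 0.67 (working memory) and 1.06 (ARENA). From protocol section 7.2: two-tailed test, 80% power, 30% attrition. Assumed, because the documents give no values: moderator prevalence of 15% to 50%, and interaction sizes set as fractions of the pilot d values.

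**1. Reproduce the plan's figure.** For d = 0.48, n per arm = 2 × (1.96 + 0.84)² / 0.48², which rounds up to 69. Dividing by 0.85 gives 82. The t-test version gives 70, then 83. The SAP's 84 is reproduced to within two participants per arm. After attrition, 84 × 0.85 = 71.4 per arm, and power at d = 0.48 is 0.81 to 0.82. So 168 is right for main effects at 15% attrition, with little to spare.

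**2. Binary moderator.** With 1:1 arms, n per arm analysed and prevalence p, in SD units:

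SE(interaction) = sqrt(2/n) / sqrt(p(1 − p))

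At n = 71, sqrt(2/71) = 0.168. Detectable interaction at 80% power = 2.80 × SE. Power for interaction δ = Φ(δ/SE − 1.96).

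| Prevalence (assumed) | SE | Detectable interaction | Power, δ = 0.67 | Power, δ = 0.53 | Power, δ = 1.06 |
|---|---|---|---|---|---|
| 50% | 0.336 | 0.94 | 0.514 | 0.352 | 0.885 |
| 30% | 0.366 | 1.03 | 0.448 | 0.304 | 0.825 |
| 20% | 0.420 | 1.18 | 0.358 | 0.243 | 0.714 |
| 15% | 0.470 | 1.32 | 0.296 | 0.203 | 0.616 |

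Here δ = 0.67 means the moderator abolishes the pilot working-memory effect, 0.53 that it halves the ARENA effect, and 1.06 that it abolishes the ARENA effect. Only the last reaches 80%, and only once prevalence is somewhere between 25% (0.781) and 30% (0.825). At 50% prevalence the detectable 0.94 is 0.94/1.06 = 89% of the whole pilot ARENA effect.

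**3. Continuous moderator.** SE per moderator SD = 2/sqrt(142) = 0.168, so the detectable interaction is 2.80 × 0.168 = 0.47 SD per SD. This applies to white matter lesion load, processing speed and mood scores if everyone analysed has the measure. Section 7.5.2 acquires FLAIR only if scan time allows, so the number for HE.1 could be smaller.

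**4. Sensitivity.**
- *30% attrition* (117 analysed): 1.04 SD at 50% prevalence, 1.13 at 30%, 1.45 at 15%; continuous 0.52 per SD.
- *Multiplicity:* the SAP plans Benjamini-Hochberg adjustment for simultaneous hypotheses. A Bonferroni split over three moderators, used as a conservative stand-in, raises the 142-participant figures to 1.09 SD (50%) and 1.25 SD (25%).
- *Baseline adjustment* works the other way. If covariates explain 30% of variance (illustrative), 0.94 × sqrt(0.70) = 0.79 SD at 50% prevalence. SE becomes 0.336 × 0.837 = 0.281, and power for δ = 0.67 is Φ(0.67/0.281 − 1.96) = about 66%, still short of 80%.

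**5. Size needed.** To detect a binary-moderator interaction of 0.67 with 80% power at 15% attrition, total enrolment would have to be 330 (50% prevalence) to 439 (25%).

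Nothing was calculated for mediation, and the documents give no inputs for it.

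**The case against.** The strongest reply is that Aim 3 is labelled exploratory throughout, so formal power is not required, and that the protocol itself says the trial was powered for Aims 1 and 2. That is fair, and it limits the weight of the point. It does not support the SAP sentence: an aim that needs no power should not be promised any, and the SAP goes beyond the protocol here.

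A second reply is that the calculation is too harsh. The planned model adjusts for baseline, and several candidate moderators are continuous. Both points stand and are reflected above. The 0.94 to 1.32 SD range belongs to binary moderators at assumed prevalences without adjustment and should not be applied to lesion load. The SAP also expects effects after 12 weeks to exceed those of the two-week pilot, but it gives no figure, and a larger main effect does not imply a larger interaction.

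Three stronger readings are tempting, and the documents do not support them:
- *The design cannot answer Aim 3.* Low power limits precision; it does not make an exploratory question unanswerable. Very large binary interactions and moderate continuous ones are detectable.
- *The entry rules defeat HE.2.* The exclusions remove only uncontrolled or severe disease. Participants with stable hypertension or diabetes remain eligible, so HE.2 can be estimated as written. The vascular exclusions do not touch HE.3. No figure shows how much range is lost or whether response varies with disease control.
- *The SAP plans to read a null as no moderation.* It says only what a significant interaction implies. The risk is that its power assurance invites that reading.

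**Conclusion.** The assurance about Aim 3 is unsupported. For binary moderators it is untrue unless the moderator removes nearly all of an effect as large as the pilot ARENA d = 1.06, itself estimated from 8 active and 5 sham participants. More ordinary moderation has power of at most 51% (working-memory effect abolished) or 35% (ARENA effect halved). Continuous moderators fare better, at about 0.47 SD per SD.

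These figures rest on 71 per arm, a two-sided 5% test, an unadjusted SD of 1 and assumed prevalences. Higher attrition or multiplicity adjustment worsens them. Baseline adjustment improves them, but at the illustrative 30% of variance explained, power to detect abolition of the working-memory effect still falls short of 80%.

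The sizing for Aims 1 and 2 is not in question here at the SAP's own attrition rate. On HE.2 only a minor scope note follows: conclusions apply to the range of vascular disease actually enrolled.

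**What to change.** In the SAP (Sample Size Determination/Power Analysis), delete the Aim 3 assurance and substitute text along these lines:

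*The sample size was set for the main treatment effects in Aims 1 and 2. Aim 3 is hypothesis-generating. With 142 participants analysed (15% attrition), two-sided 5% and a residual SD of 1, the interaction detectable with 80% power is about 0.94, 1.03 and 1.32 SD for a binary moderator with assumed prevalence 50%, 30% and 15%, and about 0.47 SD per SD for a continuous moderator. No power is claimed for mediation.*

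The sponsor should insert its own expected prevalences and residual SD, and use one attrition rate once the SAP's 15% and the protocol's 30% are reconciled. A power statement for mediation should appear only if one is calculated.

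In the SAP (Analysis for Exploratory Aim 3), add that interactions will be reported as estimates with 95% confidence intervals and that a non-significant interaction will not be read as evidence of no moderation. Add one sentence limiting HE.2 conclusions to the enrolled range; HE.2 itself need not be rewritten.

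The change is to wording only. Sample size, conduct and the Aim 1 and 2 analyses are unaffected. The price is a less favourable statement about an exploratory aim.
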